#### **Treatment-related Adverse Event**

A treatment-related AE is any AE reported on the ADVERSE EVENTS eCRF that is marked as definitely related, or possibly/probably related to study drug.

#### Treatment-Emergent Laboratory, Vital Signs, ECGs, and ECHO Abnormality

A treatment-emergent laboratory, vital signs, ECGs, and ECHO abnormality will be defined as any laboratory, vital signs, ECGs, and ECHO abnormality occurring or worsening after the initiation of eteplirsen dosing and within 28 days of the last dose of eteplirsen.

#### **Prior Medication**

A prior medication will be any medication taken and completed prior to the first dose of eteplirsen.

#### **Concomitant Medication**

A concomitant medication will be any medication that is taken in the time period starting with the initiation of the first dose of eteplirsen dosing and ending within 28 days after the last dose of eteplirsen.

#### Time since DMD Diagnosis

The time since DMD diagnosis, in months, will be calculated as (Day 1 - Date of DMD diagnosis + 1)/30.4375.

#### **Duration of Corticosteroid Treatment**

The duration of corticosteroid treatment, in months, will be calculated as (Day 1 - Date on which the patient started corticosteroid treatment + 1)/30.4375.

#### **Corticosteroid Schedule**

Corticosteroid schedules will include continuous (daily) or other (including intermittent dosing such as Saturday and Sunday dosing only).

#### EudraCT Category

- In utero: Unborn infants, still in the womb.
- Preterm newborn: Subjects born before 37 weeks from their conception.
- Newborns: Newborn aged from birth to less than 28 days.
- Infants and toddlers: Subjects aged 28 days to less than 2 years.
- Children: Subjects aged 2 to 11 years.
- Adolescents: Subjects aged 12 to less than 18 years.

- Adults: Subjects aged 18 to 64 years.
- Adults: Subjects aged 65 to 84 years.
- Adults: Subjects aged 85 years and over.

#### 5.8. **Programming Conventions**

This section details general conventions to be used for the production of tables, figures and listings. Departures from these general conventions will be specified in appropriate sections.

- For continuous or quantitative variables, mean and median values will be formatted to 1 more decimal place than the measured value on the eCRF or provided file by vendor. Standard deviation and standard error values will be formatted to 2 more decimal places than the measured value on the eCRF. Minimum and maximum values will be presented with the same number of decimal places as the measured value on the eCRF. Percentages will be presented with 1 decimal place.
- For categorical variables, the number and percentage of a category will be presented in the form XX (YY.Y%), where the percentage is YY.Y.
- Percentages of patients with treatment-emergent abnormalities will be based on non-missing values unless stated otherwise.
- Study Day will appear in the data listings as appropriate.
- Date variables will be formatted as DDMMMYYYY for presentation.
- SAS® Version 9.4 or higher will be the statistical software package used for all analyses unless otherwise specified.
- The Clinical Data Interchange Standards Consortium (CDISC) Analysis Data Model Implementation Guide V1.1 for preparing data sets will be used for this study.
- The CDISC Study Tabulation Model Implementation Guide V3.2 for preparing data sets will be used for this study.
- Tables, figures, and listings will be presented in landscape orientation.
- Listings will be sorted by cohort, patient and then date unless otherwise specified.

## 6. STATISTICAL ANALYSES

## 6.1. Patient Disposition

For Study 4658-102, the number of patients enrolled, the number in Safety Set, the number and percentage of patients completing the study through Week 96, the number and percentage of patients prematurely discontinuing before Week 96, and the duration of study (weeks) will be summarized. Reasons for premature discontinuation will also be summarized. All analyses will be performed overall and by age cohort.

Patient eligibility and disposition will be presented in a listing.

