8.4. Completion of a Patient's Participation in the Study

Patients are considered completers for the purpose of analysis once the Week 48 assessments have been completed. Patients may continue in the study up to and including 96 weeks based on the judgement of the Investigator (described further in Section 7.1); however, a Safety Follow-up visit will occur approximately 4 weeks after the last dose administered regardless of the patient's duration in the study. The length of a patient's participation will be from the time the informed consent form is signed until completion of the Safety Follow-up visit (approximately 4 weeks after the last dose is administered).

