13. STATISTICS

13.1. General Considerations

This section describes the rules, conventions, statistical analysis, and presentation of data for this study. Full details will be provided in the Statistical Analysis Plan (SAP) for this study.

Revisions during the study may be made to accommodate protocol amendments and to make changes to adapt to unexpected issues in study execution that could affect planned analyses. A formal SAP for the analysis and presentation of data from this study will be prepared and issued before database lock. The SAP will provide a more technical and detailed description of the proposed data analysis methods and procedures. Deviations from the statistical analyses outlined in this protocol will be included in this plan; any further modifications will be noted in the clinical study report (CSR). All statistical analyses will be performed by or under supervision of the Sponsor.

All available data will be included in data listings and tabulations. No imputation of values for missing data will be performed. Percentages of patients with AEs or laboratory abnormalities will be based on non-missing values.

All data collected in this study will be presented using summary tables and patient data listings. Summary statistics for raw and change from baseline data of continuous variables will minimally include n, mean, standard deviation, minimum, median, and maximum. For categorical variables, frequencies and percentages will be presented. Graphical displays will be provided as appropriate.

Endpoints will be assessed primarily using simple descriptive statistics and/or inferential statistics. Baseline will generally be defined as the last available value before dosing.

The primary analysis will be done using the Week 48 data. In addition, all data through the end of study will also be analyzed.

13.2.

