13.5. Disposition, Demographics, and Baseline Characteristics

The number and percentage of patients completing the study through Week 48 (ie, completers) or prematurely discontinuing before Week 48 will be summarized. Disposition will also be summarized over the entire 96-week duration of the study. Reasons for premature discontinuation will also be summarized.

Demographic characteristics including age (years), race, ethnicity, and baseline characteristics including height/length (cm), and weight (kg) will be summarized by age cohort and overall. Demographic data and baseline characteristics will be presented in data listings.

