13.8.2.2. Physical Examinations, Vital Signs, Height, and Weight

Vital signs, height/length, and weight will be presented by visit for each age cohort and overall, summarizing the actual values and change from baseline to each visit for each parameter using descriptive statistics. Frequency tables of predefined change to abnormal in vital sign values will be generated.

Data obtained from physical examinations will be presented in patient data listings. Any clinically significant findings will be recorded as AEs.

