13.8.2.3. Clinical Safety Laboratory Tests

Clinical chemistry, hematology, renal function, coagulation, and urinalysis will be presented by visit for each age cohort and overall, summarizing the actual value and change from baseline to each visit for each parameter using descriptive statistics for each continuous, and frequency tables for each discrete parameter. Frequency tables of predefined change to abnormal of select laboratory parameter values will be generated.

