13.11. Interim Analysis

An interim analysis of the PK and safety data following completion of dose escalation for one or both age cohorts may be done for administrative purposes. Detailed plans for data analysis will be documented in the study SAP or in a separate SAP for interim analysis only.

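### SAP 6.1 gives disposition at Week 96 only, although the protocol's primary analysis and completer definition are at Week 48; SAP 7.1 does not declare this, and the readable SAP shows no Week 48 cut for its cumulative safety tables

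*SAP*

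**What the plan says.** **Protocol.** Section 13.1 sets the order of the analyses: "The primary analysis will be done using the Week 48 data. In addition, all data through the end of study will also be analyzed". Section 8.4, repeated in footnote a of Table 2, fixes the completer definition: "Patients are considered completers for the purpose of analysis once the Week 48 assessments have been completed". Section 13.5 asks for two disposition summaries. The first is at Week 48: "The number and percentage of patients completing the study through Week 48 (ie, completers) or prematurely discontinuing before Week 48 will be summarized". The second is additional: "Disposition will also be summarized over the entire 96-week duration of the study".

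On safety, 13.8.2.1 lists the TEAE and SAE tables. Section 13.8.2.2 adds "Frequency tables of predefined change to abnormal in vital sign values will be generated" and 13.8.2.3 adds "Frequency tables of predefined change to abnormal of select laboratory parameter values will be generated". The only interim analysis is in 13.11: "An interim analysis of the PK and safety data following completion of dose escalation for one or both age cohorts may be done". Section 13.1 also requires the SAP to record departures from the protocol's analyses.

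**SAP.** Section 6.1 summarises completion through Week 96 and "the number and percentage of patients prematurely discontinuing before Week 96", with reasons and duration of study; it has no Week 48 count. Section 6.8.1 bases the AE tables on all data collected. Section 5.7 lets treatment-emergent abnormalities run to 28 days after the last dose. Section 7.1 names removal of the interim analysis as the only change from the protocol.

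**The concern.** The protocol's primary time point does not appear in the SAP's disposition section, and the SAP tells its reader that nothing but the interim analysis has changed. Two consequences follow.

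First, the report could use a different meaning of completion from the protocol's. Treatment after Week 48 is optional, so stopping at Week 48 is a planned outcome. A table that recognises only Week 96 cannot separate it from early discontinuation.

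Second, cumulative safety percentages over all data mix patients followed to about Week 48 with patients followed to Week 96. Protocol 7.1 lets the Investigator continue a patient on the absence of a safety signal and an indication of benefit, so the later follow-up is selected. A Week 48 cut puts completers on a common follow-up period.

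**Working it through.** The plan gives no figure to reproduce. The main check compares the texts.

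| Item | Protocol | SAP |
|---|---|---|
| Primary time point | Week 48 (13.1) | Readable 4.4 describes only DMC review and the final analysis |
| Completer | Week 48 assessments done (8.4) | Week 96 (6.1) |
| Disposition | Week 48 and 96 weeks (13.5) | Week 96 only (6.1) |
| Interim analysis | Optional look after dose escalation (13.11) | Removed (7.1) |
| Other changes | To be recorded in the SAP (13.1) | None stated (7.1) |

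The interim look follows the 10-week titration. Removing it does not account for the loss of a Week 48 disposition table.

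**Disposition.** One patient who completes Week 48 and stops is 1/12 = 8.3% overall, or 1/6 = 16.7% of a cohort of 6. The documents do not give the number of such patients.

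**Can the duration bins stand in?** SAP 5.7 defines duration on eteplirsen as (last dose − first dose + 7)/7 weeks. The nominal Week 48 infusion is Day 330, so the result is (329 + 7)/7 = 48.0 weeks, in the bin 48 to <72. If that last dose is given 3 days early, inside the protocol's window, the result is (326 + 7)/7 = 47.6 weeks, in the bin 24 to <48. The bins measure dosing, not completion.

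**Can the first-year AE tables stand in?** Nearly. One year is 365.25/7 = 52.18 weeks, and 52.18/48 = 1.087. Under a constant hazard, with x the cumulative hazard to Week 48, the difference in incidence is exp(−x) − exp(−1.087x). Its maximum is 3.1 points, at a Week 48 incidence of 62%.

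**Cumulative abnormality tables (illustration only).** Scheduled post-baseline visits, from Protocol Tables 2 and 3, leaving out early-termination and follow-up visits:

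- Full safety panel: Weeks 2, 4, 8, 12, 24, 36, 48 = 7; adding 60, 72, 84, 96 = 11.
- Renal blood and quantitative urine tests: Weeks 2–12 (11 visits) plus 10 visits to Week 48 = 21; adding 49, 60, 72, 84, 96 = 26.
- Vital signs: 48 infusion days, against up to 96.

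Assumption, not in the documents: visits are independent, each with a 1% to 10% chance p of an abnormal result. The share of patients flagged after n visits is 1 − (1 − p)^n. The gap compares everyone followed to Week 96 with everyone cut at Week 48.

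| Group | p = 1% | p = 10% | Range of gap, points |
|---|---|---|---|
| Full panel | 6.8 vs 10.5 | 52.2 vs 68.6 | 3.7 to 16.4 |
| Renal/urine | 19.0 vs 23.0 | 89.1 vs 93.5 | 4.0 to 7.8 (maximum at p = 4.2%) |
| Vital signs | 38.3 vs 61.9 | 99.4 vs 100.0 | 0.6 to 25.0 (maximum at p = 1.4%) |

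The vital-sign row counts infusion days. Footnote d of Table 3 and Protocol 10.3.2 allow two measurements per infusion instead of four after Week 48 for patients without an infusion reaction. Full dosing then gives 48 × 4 = 192 measurements to Week 48 and 192 + 48 × 2 = 288 to Week 96. That is 1.5 times as many measurements, against 2.0 times as many infusion days.

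Abnormalities that persist within a patient shrink every gap. If every affected patient is already flagged by Week 48, the gap is 0.

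**The case against.** The SAP's running header says it is for the final analysis. The protocol plans two analyses, so a plan for the second could properly leave the first to another document. Sections 4.4.2 and 5.1 have gaps, and wording in 6.4 and 6.7 suggests that other analyses were removed from the public text. The entry in SAP 7.2 that earlier-SAP changes do not apply does not show that no other plan exists. This stands, and it limits the safety-table part to moderate confidence. It does not rescue 6.1, which reads as complete and omits a table the protocol names, or 7.1, which leaves that omission undeclared.

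Much can be recovered elsewhere. By-visit summaries include Week 48, first-year AE tables come close to a Week 48 cut, and all safety data are listed. With about 12 patients, Week 48 completers could be counted from the disposition listing. This also stands, within limits: by-visit summaries are not cumulative and leave out unscheduled results (SAP 5.6), and the AE tables cover neither disposition nor abnormality frequencies.

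No readable text says how the eCRF codes a patient who stops after Week 48. Counting him as a premature discontinuation is therefore the natural reading of 6.1, not a certainty. What is certain is that 6.1 has no row showing him as a completer.

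For ECG and ECHO, Protocol 13.8.2.4 and 13.8.2.5 ask only for by-visit summaries, which the SAP supplies, so there is no shortfall there.

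**Conclusion.** The disposition finding and the inaccurate statement in SAP 7.1 hold on the text, with high confidence. Their size is 8.3 points of 12 (16.7 of 6) per patient who completes Week 48 and stops, and possibly zero in total. The absence of a Week 48 cut from the cumulative safety tables holds for the readable SAP only, with moderate confidence. The visit-count gaps rest on an assumed per-visit probability and independence. They show direction and possible scale; they are not predictions.

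A reader might infer that the sponsor has abandoned the Week 48 primary analysis, or that safety information would be lost. The documents support neither. A Week 48 plan may sit in redacted text or in another document, and SAP 6.8 puts all safety data in the listings. The study is single-arm and its safety analysis is descriptive, so the point lies between minor and should-fix.

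**What to change.** 1. **SAP 6.1.** Add the Week 48 table of completers and premature discontinuations, with reasons, as the primary disposition table. Keep the 96-week table and give patients who completed Week 48 and did not continue their own category.
2. **SAP 6.8.** Unless a separate Week 48 plan already does so, produce the protocol-named TEAE and SAE tables and the laboratory and vital-sign change-to-abnormal tables with a Week 48 date cut as primary. Keep the all-data versions as additional. For patients who continue, cut at the date of the Week 48 assessment. For patients who stop at or before Week 48, cut at 28 days after the last dose, which keeps the TEAE window of SAP 5.7. A cut by date also brings in unscheduled results. Week 48 versions of the shift, highest/lowest and ECG/ECHO abnormality tables are optional.
3. **SAP 7.1.** Correct the statement that nothing else changed, or declare and justify a move to a single end-of-study analysis. If a separate Week 48 plan exists, cite it here.

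The cost is SAP wording, one new disposition table and one rerun of existing tables with a date cut. No new data, visits or methods are needed.

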## 6.2. Demographics and Baseline Characteristics

Demographic and Baseline characteristics will be summarized overall and by age cohort. These variables will include age (months), EudraCT age category, race, ethnicity, height/length (cm), weight (kg), BMI (kg/m^2), mutation, time from DMD diagnosis (months) to Baseline, corticosteroid medication type, corticosteroid frequency, duration of prior corticosteroid use at Baseline.

Patient-level demographic data and Baseline characteristics will be presented in data listings.

## 6.3. **Prior and Concomitant Medications**

Concomitant medications will be coded by preferred term using the most recent World Health Organization (WHO) Drug Dictionary (WHODRUG, December 2013). The number and percentage of patients in the safety population taking concomitant medications will be tabulated by Anatomical Therapeutic Chemical (ATC) classification pharmacological subgroup and WHO drug preferred term by cohort. At each level of summarization, a patient is counted once if he/she reported one or more medications at that level. The summarization of concomitant medications for the Study 4658-102 final analysis will include all concomitant medications collected at the time of the Study 4658-102 data lock.

All prior medications and concomitant medications will be presented in data listings.

## 6.4. Medical History

Medical history data for the safety set will be presented in data listings. The summarization will only be included for the Study 4658-102 final analysis

## 6.5. Physiotherapeutic Interventions

A listing of all physiotherapeutic interventions will be provided.

## 6.6. **Protocol Deviations**

A listing of major protocol deviations will be provided. The protocol deviations will be identified based on a review of the study data prior to the database lock and will include the nature of the deviation (e.g. inclusion/exclusion, prohibited therapies). Additionally, major deviations will be summarized by deviation type. The listing and table will be summarized separately by whether the protocol deviations are related to COVID-19 or not.

## 6.7. Exposure to Study Drug

The exposure to eteplirsen will be summarized for eteplirsen-treated patients in the Safety Analysis Set. The variables will include the following (as applicable): total number of infusions received, total number of infusions on 30 mg/kg of eteplirsen received, cumulative amount of drug received (mg), duration on eteplirsen in 24-week intervals, and patient years on eteplirsen. For both the 4658-102 final analyses, these endpoints will be calculated cumulatively

Patient-level study drug information will be provided in a data listing. Additionally, a listing of the derived exposure parameters above will be generated as well as a listing of overdoses. The actual dose will be compared to the planned dose. Any actual dose that is greater than 1.10 times of the planned dose will be considered an overdose. Planned dose is calculated as the dose level in mg/kg multiplied by the patient's most recent weight prior to the dose (or on the same day with no time).

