9.2. Treatments Administered

Eligible patients will receive a once weekly IV infusion of eteplirsen for up to 96 weeks. Eteplirsen should be prepared for dosing by following the steps detailed in the study-specific Pharmacy Manual.

The starting dose is 2 mg/kg eteplirsen, with escalation to 4, 10, 20, and 30 mg/kg over the course of the dose-titration period.

The following guidelines for the timing of dosing should be followed throughout the study:

- Patients should receive Eteplirsen once every 7 days starting on Week 1. A window of ± 3 days from the scheduled dose is acceptable after the first infusion.
- Patients may not receive 2 separate doses of Eteplirsen within the same 60-hour period.
- The Medical Monitor should be contacted in the event of ≥2 consecutive missed doses.

The administered dose is calculated by patient weight, which will be collected on a weekly basis and used to calculate the dose to be administered at the next visit(s). For example, the weight collected at Week 2 will be used to calculate the doses to be infused during the Week 3 visit.

Eteplirsen should be diluted in a normal saline, where the final volume, after eteplirsen has been added, equals the volume appropriate for the patient's weight. The drug delivery bag, syringe or flask is to be labeled in accordance with standard pharmacy practice and to include total volume as well as drug dose in milligrams. Eteplirsen will be diluted in normal saline to a total volume per Table 5 and infused IV for approximately 35 to 60 minutes using an infusion or syringe

pump. It is recommended that a topical anesthetic cream be applied to the infusion site prior to each administration of eteplirsen.

Table 5: Example Eteplirsen Dilution Scheme

Patient Weight	Total Eteplirsen Dose (30 mg/kg)	Total Volume of Eteplirsen Drug Product	Dilution in Saline up to Total Volume of:	Maximum Eteplirsen Concentration in Infusion
<5 kg	<150 mg	<3 mL	10 mL	15 mg/mL
5 to 10 kg	150 to 300 mg	3 to 6 mL	15 mL	20 mg/mL
10 to 15 kg	300 to 450 mg	6 to 9 mL	25 mL	18 mg/mL
15 to 25 kg	450 to 750 mg	9 to 15 mL	50 mL	15 mg/mL
>25 kg	>750 mg	>15 mL	100 mL	

Note: Refer to the Pharmacy Manual for other dosing dilution schemes.

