11.6. Special Situations

11.6.1. **Overdose**

An overdose is defined as administration of a dose that is >10% higher than the assigned dose per the protocol. An overdose is not an AE. An overdose will be reported even if it does not result in an AE. An overdose will be recorded on the appropriate form and sent to the Sponsor or designee within 24 hours.

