## 5.7. Algorithm, Computation and Definition of Derived Variables

#### Day 1

Day 1 in Study 4658-102 will be defined as the date of the first eteplirsen administration in Study 4658-102.

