#### Planned Dose and Overdose

The body weight-based planned dose was calculated based on most recent weight of previous visits. When calculating the planned dose, the body weight is rounded to a single decimal using conventional rounding rules. While in preparing actual dose, an unconventional rule is applied for calculating the volume of the concentrated drug (50 mg/mL) in milliliter. Any volume of 0.1 or above is rounded up (e.g. 25.14 mL is rounded up to 26 mL) and any volume below 0.1 is rounded down (e.g. 25.09 mL is round up to 25 mL. The overdose is defined as any actual dose >10% above the planned body weight-based dose.

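### SAP 5.7 and 6.7 take planned dose from different weights for the same >10% overdose test

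*SAP*

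**What the plan says.** The SAP defines planned dose twice.

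- SAP 5.7, headed "Algorithm, Computation and Definition of Derived Variables", states under Planned Dose and Overdose: "The body weight-based planned dose was calculated based on most recent weight of previous visits". Weight is rounded to one decimal, and an overdose is an actual dose more than 10% above planned. On preparation, it says that "an unconventional rule is applied for calculating the volume of the concentrated drug (50 mg/mL) in milliliter": a fraction of 0.1 mL or more goes up to the next whole mL, and a smaller fraction goes down.
- SAP 6.7 orders the overdose listing with the same 1.10 threshold. It restates planned dose as dose level times the "most recent weight prior to the dose (or on the same day with no time"). It does not mention rounding the weight.

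The protocol bears on which weight is right.

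- Section 9.2 has weekly weights set the dose at the following visit, and gives an example: "the weight collected at Week 2 will be used to calculate the doses to be infused during the Week 3 visit".
- Section 11.6.1 defines an overdose as "administration of a dose that is >10% higher than the assigned dose per the protocol".
- Table 2 and section 10.3.3 have weight measured before infusions. Table 2 makes it weekly.

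Protocol 13.7 plans no overdose listing. This is therefore a conflict within the SAP, and not an undeclared departure from a protocol-planned analysis.

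**The concern.** A weight taken on the dosing day is not a weight from a previous visit, so a programmer cannot follow both sections, and the SAP does not say which governs. A dosing-day weight will usually exist. If it is timed before the infusion, it is the latest weight before the dose. If it has no time, the bracketed clause in 6.7 admits it. Where sites dose as Protocol 9.2 directs, 6.7 then tests the infusion against a weight that did not set the dose.

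Two programmers working from the same SAP could list different infusions as overdoses. The listing matters to a reader of a safety study in children aged 6 to 48 months, but nothing else depends on this derivation. Site reporting of overdoses within 24 hours, the AE tables, the exposure summaries and the stopping rules are unaffected.

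**Working it through.** **Inputs.** Vial strength 50 mg/mL, volume rounding and the 1.10 threshold come from SAP 5.7. Dose levels of 2, 4, 10, 20 and 30 mg/kg come from Protocol 9.2. Weights of 5.0 to 25.0 kg in 0.1 kg steps (201 values) span the three middle bands of Protocol Table 5 ("Example Eteplirsen Dilution Scheme"). The documents give no patient weights, so visit-to-visit differences of 0.1 to 0.3 kg are an assumption.

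**Formulas.** The dose is prepared from the previous-visit weight.

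- Volume = dose level × previous weight / 50, rounded by the SAP 5.7 rule. The rule as coded reproduces the SAP's own examples (25.14 mL to 26 mL, 25.09 mL to 25 mL).
- Actual dose = 50 × rounded volume.
- Ratio under 5.7 = actual / (dose level × previous weight).
- Ratio under 6.7 = actual / (dose level × same-day weight).
- An infusion is listed if its ratio exceeds 1.10.

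**Two cases at 30 mg/kg.**

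- Previous 9.0 kg, same-day 9.1 kg. Volume 30 × 9.0 / 50 = 5.4 mL, prepared as 6 mL = 300 mg. Under 5.7: 300/270 = 1.111, listed. Under 6.7: 300/273 = 1.099, not listed.
- Previous 10.7 kg, same-day 10.6 kg. Volume 30 × 10.7 / 50 = 6.42 mL, prepared as 7 mL = 350 mg. Under 5.7: 350/321 = 1.090, not listed. Under 6.7: 350/318 = 1.101, listed.

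**All 201 weights at 30 mg/kg.** The entries are numbers of weights at which 6.7 gives a different result from 5.7.

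| Difference in weight | Same-day higher: entry dropped | Same-day lower: entry added |
|---|---|---|
| 0.1 kg | 6 | 7 |
| 0.2 kg | 12 | 14 |
| 0.3 kg | 17 | 22 |

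At 0.1 kg, entries drop at 6.0, 7.5, 9.0, 10.6, 12.1 and 13.6 kg. They are added at 6.1, 7.6, 9.1, 10.7, 12.2, 13.7 and 15.2 kg. No weight above 15.2 kg is sensitive to 0.1 kg.

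**Other dose levels, 0.1 kg (dropped / added).** 20 mg/kg: 7 / 8. 10 mg/kg: 4 / 4. 4 mg/kg: 2 / 2. 2 mg/kg: 1 / 1.

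**Without whole-mL rounding.** The actual dose equals the 5.7 planned dose, so 5.7 lists nothing. The 6.7 ratio becomes previous weight / same-day weight, which exceeds 1.10 only if weight falls by more than 1 − 1/1.10 = 9.1%. A 0.3 kg fall from 5.0 kg is 6.0%, so 0 of 201 weights are affected by any difference up to 0.3 kg. Protocol 10.3.3 requires re-weighing above a 10% change.

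**Rounding alone.** With the previous-visit weight used throughout, correctly prepared doses already exceed 1.10 at 32 of 201 weights at 30 mg/kg, 62 at 20, 118 at 10, 154 at 4 and 178 at 2 mg/kg.

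**The case against.** There are three serious points on the other side.

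1. *The protocol does not speak with one voice.* Section 10.3.3 says the pre-infusion weight serves to determine the volume given, which can be read as same-day dosing. If a site worked that way, 6.7 would test against the right weight for that site. This stands as a caution: calling an entry missed or false assumes that 9.2 was followed. But 9.2 is explicit and has a worked example, while 10.3.3 does not say which visit's dose the weight sets. Even on the same-day reading, 5.7 and 6.7 still contradict each other.
2. *The size depends on the rounding rule.* Without it the count is 0 of 201. The SAP's examples of about 25 mL correspond to roughly 42 kg at 30 mg/kg (25.14 × 50 / 30 = 41.9), well above the weights examined here, and Protocol Table 5 defers other dilution schemes to the Pharmacy Manual, which was not available. This stands as a limit on the size. The rule is nevertheless current SAP text with no weight restriction.
3. *If the rounding does apply, it outweighs the choice of weight.* At 30 mg/kg it flags 32 weights by itself, against 6 or 7 changed by a 0.1 kg difference. This is correct, and settling the weight definition does not cure it.

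None of these reconciles the two sections.

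**Conclusion.** The concern holds as a minor inconsistency. SAP 5.7 and 6.7 set incompatible planned doses for one test, and Protocol 9.2 and 11.6.1 support 5.7. As written, 6.7 can leave an infusion off the overdose listing or put one on it wrongly. If the SAP's whole-mL rounding applies at these body weights, a 0.1 kg difference is enough at 6 (dropped) or 7 (added) of 201 weights at 30 mg/kg. If it does not apply, a fall of more than 9.1% between visits is needed.

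These are counts of weights, not expected error rates; the documents do not allow an error rate to be derived. Confidence is high that the sections conflict. The direction of each misclassification rests on sites having dosed from the previous visit's weight.

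**What to change.** In SAP 6.7, replace the sentence defining planned dose with a reference to the definition in 5.7, and delete the clause that admits an untimed same-day weight. A cross-reference is better than restating the rule, because it also carries over the one-decimal rounding of weight that 6.7 omits. Before finalising, check the dosing records to confirm that sites used the previous visit's weight, as Protocol 9.2 directs.

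The cost is one SAP sentence and a small programming change. No new data are needed, since weight is already collected weekly. Entries caused only by whole-mL rounding will remain in the listing.
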